5.3 Procedures During Treatment

After enrollment and consent, a specific order will be placed in the electronic medical record for this study's purposes. This order will alert IDS that a patient has been enrolled and the patient will be randomized accordingly. After randomization, IDS will send to the floor either 5 doses of placebo or furosemide clearly marked for the specific patient. A research coordinator will be present at this time and ensure that there are 5 doses of furosemide/placebo and that the patient's nurse is aware that the patient is enrolled in the study. The research coordinator will also ensure that the medication order is given by postpartum day 1 and ensures that the first pill is given after 6 hours from delivery. Patients in the furosemide arm will be assigned to receive oral furosemide 20 mg/day for a total of 5 consecutive days during hospitalization and after discharge. This dose of furosemide is based on prior studies,3 which have shown it to be safe with breast feeding. For those randomized to the placebo group, they will be given placebo pills for a total of 5 consecutive days. The time of initiation of first pill given will be recorded by the research coordinator. Each time a pill is given in the hospital, it will be accounted for in the medical administration record (MAR) in the EMR. Pills should be given approximately 24 hours apart, and the Epic order placed after enrollment will have this distinction.

Patients in both groups will undergo similar postpartum surveillance, including blood pressure and pulse assessment every 4 hours and urinary output measurements while hospitalized. Proper treatment for elevated blood pressures will be initiated immediately as soon as the elevated blood pressures are recognized, and will not be delayed for any study purposes including study drug administration. For this study, antihypertensive therapy will be initiated for persistently elevated postpartum blood pressures (BP) of ≥ 150 systolic or >100 mg Hg diastolic with 5 mg of amlodipine PO. Persistent severe range blood pressures (BP >160 mm Hg systolic or >110 mm Hg diastolic) will be treated with IV antihypertensives if needed, as well as 10 mg of amlodipine PO. If further antihypertensive medications are needed to maintain blood pressures <150/100, these will be per the discretion of the clinical staff in both arms. All physicians and clinical staff in Labor and Delivery as well the postpartum unit will be educated extensively to avoid diuretic antihypertensive medications unless deemed medically necessary. Furthermore, diagnostic and laboratory tests will be per the discretion of the clinical staff in both arms as well. Routinely, all patients undergoing cesarean section remain hospitalized for at least 3 days and all patients with preeclampsia with severe features are kept in the hospital for 3 days (per the recommendations of the ACOG Task Force on Hypertension in Pregnancy). 10 All patients will be followed at for 10 days after discharge as detailed below. Being enrolled in the study will not change the patient's clinical care at any time. Physicians, staff, and patients will be blinded to the intervention administered, unless a break in blinding is required for medical intervention of adverse effects.

5.4 Follow-up Procedures

Prior to patient discharge, a research coordinator will ensure that the patient has the correct amount of pills left and will review instructions about taking the pill daily for however many remaining doses there are. If patients are breastfeeding exclusively, the

research coordinators will ask the patients upon discharge if they encountered any difficulties with breastfeeding while in the hospital. Patients will be followed for 10 days after discharge through Heart Safe Motherhood, a texting program offered at the Hospital of University of Pennsylvania in which women with HDP take their own blood pressures at home, and report those blood pressures through a texting service. A physician who is part of the study, will review the blood pressures daily and notify patients if more blood pressures, medications, or medical attention are needed. All patients in the study will be asked to text through the program their daily blood pressure and an affirmation that they are taking the remaining daily doses of furosemide/placebo at home. All patients, regardless of whether they are in the study or not, are expected to have a 6 week postpartum appointment. Participants will be asked to bring any remaining pills with them to that appointment at which time a research coordinator will collect the remaining pills, and record how many doses were missed. Any pills brought back by the patient will be given back to IDS to dispose of them. The research coordinator will also ask questions regarding any breastfeeding issues at this time. Furthermore, the charts of breastfed neonates will be followed to determine NICU admission or readmission during the first 6 weeks postpartum.

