4.2 Toxicities and Dosing Delays/Dose Modifications

Any patient who receives treatment will be evaluable for toxicity. Each patient will be assessed for the development of toxicity according to development of ototoxicity or symptomatic derangements in electrolytes as determined by symptoms and corresponding daily basic metabolic profiles. In the event of the development of either, the medication will be discontinued.

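### The toxicity stopping rule has no scheduled symptom enquiry behind it once women are dosing at home, and sections 4.2 and 5.3 disagree on laboratory tests

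*Combined protocol and SAP*

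**What the plan says.** Section 4.2 assesses every treated woman for "development of ototoxicity or symptomatic derangements in electrolytes as determined by symptoms and corresponding daily basic metabolic profiles". It then says: "In the event of the development of either, the medication will be discontinued". These are two alternative triggers. Only the electrolyte trigger refers to laboratory values. Section 2.3.2.6 lists adverse effects of furosemide as a secondary endpoint, and section 9 names sustained potassium below 3.0 on treatment as an issue of concern.

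Under section 5.3, drug is given "for a total of 5 consecutive days during hospitalization and after discharge", so part of the course is taken at home. The same section says that "diagnostic and laboratory tests will be per the discretion of the clinical staff in both arms as well".

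After discharge, section 5.4 has women "text through the program their daily blood pressure and an affirmation that they are taking the remaining daily doses". A study physician reviews the blood pressures each day and can advise medication or medical attention. At 6 weeks, well after the last dose, a coordinator collects leftover pills and asks about breastfeeding.

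**The concern.** The stopping rule needs information that the home phase does not schedule. Neither hearing nor electrolyte symptoms are asked about while home doses are being taken, and no home blood draw is described. The physician who reads the daily texts is shown a blood pressure and a dosing confirmation, neither of which would reveal tinnitus, cramps or palpitations.

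Two things are at stake. The first is individual safety: a woman with a non-serious effect may keep taking drug, or report it only when the course is over. The second is ascertainment of endpoint 2.3.2.6: a low reported rate could partly reflect that nobody asked.

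Separately, 4.2 speaks of daily profiles while 5.3 makes laboratory tests discretionary. Staff cannot tell from the text which applies, even for inpatients, and the potassium concern in section 9 needs measured values.

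**Working it through.** The plan gives no figure to reproduce. The check has two parts.

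**1. What is scheduled, section by section**

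| Section | What it provides | Symptom enquiry at home? | Laboratory test at home? |
|---|---|---|---|
| 4.2 | Stopping rule based on symptoms and daily profiles | None specified | Implied by "daily" profiles for each patient, but no procedure |
| 4.4, 5.6 | End treatment for unacceptable events or toxicity | No; act once an event is known | No |
| 4.5, 5.4 | Daily blood pressure, dosing confirmation, physician review and advice | No | No |
| 5.3 | Laboratory tests at clinical discretion | No | None described |
| 5.7 | List of mandatory events for 24-hour reporting to the DSMB | No; reporting | No |
| 7.1, 7.4 | Follow-up and reporting of adverse events | No; follow-up and reporting | No |

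No section schedules a question about symptoms between discharge and the last dose.

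**2. How many doses fall at home**

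Inputs:
- Five daily doses (4.1).
- The coordinator ensures that "the medication order is given by postpartum day 1 and ensures that the first pill is given after 6 hours from delivery" (5.3), so the first dose falls on postpartum day 0 or day 1.
- Stay: "all patients with preeclampsia with severe features are kept in the hospital for 3 days", and "all patients undergoing cesarean section remain hospitalized for at least 3 days" (5.3).

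Formula: last dose day = first dose day + 4. Home doses = last dose day − discharge day, plus 1 if the discharge-day dose is taken at home.

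| Discharge day | First dose day 0 (last dose day 4) | First dose day 1 (last dose day 5) | Range of 5 |
|---|---|---|---|
| 3 (stated) | 4 − 3 = 1, or 2 | 5 − 3 = 2, or 3 | 1–3 (20–60%) |
| 2 (assumed; no stay is stated for other women) | 4 − 2 = 2, or 3 | 5 − 2 = 3, or 4 | 2–4 (40–80%) |
| 4 (assumed; longer cesarean stay) | 4 − 4 = 0, or 1 | 5 − 4 = 1, or 2 | 0–2 (0–40%) |

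These are doses taken without a scheduled symptom enquiry, not missed toxicities. The documents give no symptom rates, so no count of missed events can be derived.

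The existing text contact is long enough to carry a symptom item. In the latest case above (last dose day 5, discharge day 2), the day after the last dose is day 6, or 6 − 2 = 4 days after discharge. Texting runs for 10 days after discharge.

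**The case against.** The other side has real points.

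- **Routes exist at home.** A study physician is in daily contact and can advise medical attention. Sections 4.4 and 5.6 allow treatment to end for adverse events without a laboratory value. Section 7.1 follows every adverse event whatever its cause, and 7.4.2 covers routine reporting of non-serious events. This stands, but each route starts from an event someone already knows about.
- **The schedule table proves little.** Section 5.5 has no adverse-event, symptom or laboratory row, but it is a summary. It also leaves out the baseline adverse-event assessment, the physical examination and the 6-week pill count, all specified elsewhere. Likewise, the scheduled times in 7.1 concern reporting, for which 7.4.2 gives annual timing. Neither is relied on here.
- **The discretion sentence in 5.3 sits among inpatient procedures.** This is fair. It makes the conflict with 4.2 clearest in hospital; for the home phase the point is simply that no test is described.
- **Some material is not visible.** Consent pages were removed, and neither the DSMB attachment nor the texting program's own script can be seen. Any of them might tell women when to call. That would help safety but would not by itself make collection of the endpoint systematic or settle 4.2 against 5.3.
- **Risk is low.** The dose is 20 mg by mouth for five doses, and section 3.2 excludes potassium below 3, chronic kidney disease or creatinine above 1.2, prior diuretics and ototoxic agents. This stands and limits the weight of the point.

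A reader might infer that the stopping rule cannot work at all after discharge. The documents do not support that: ototoxicity needs no metabolic profile, and a volunteered symptom can lead to discontinuation. A reader might also infer that laboratory cover is complete in hospital and absent only at home. That would require 4.2 to govern inpatients and 5.3 to govern outpatients, which the plan does not say.

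**Conclusion.** The point holds in a limited form. During home dosing, non-serious toxicity is found only if the woman volunteers it, so the 4.2 rule and endpoint 2.3.2.6 rest on passive reporting for about 1 to 3 of 5 doses with the stated 3-day stay. That range depends on the first dose falling on day 0 or 1 and on where the discharge-day dose is taken; other discharge days are assumptions. The disagreement between 4.2 and 5.3 on laboratory tests is a separate inconsistency that also affects inpatients.

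The primary endpoint is unaffected. It would be tempting to conclude that toxicity is being missed or that the comparison of arms is biased. Neither follows: there are no event rates to work from, and the trial is double-blind with the same follow-up in both arms. This is a worthwhile, inexpensive improvement to safety and ascertainment, not a flaw that undermines the trial.

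**What to change.** 1. **Section 5.4:** add one fixed yes/no item to the daily text, through the day after the last dose, covering hearing change or tinnitus, dizziness or fainting, palpitations, and cramps or marked weakness.
2. **Response:** the reviewing study physician calls any woman who answers yes and uses clinical judgement to decide on a metabolic profile and on discontinuation under 4.2. There should be no automatic hold. These symptoms are nonspecific postpartum, and with few doses left a hold pending a blood test could end the course needlessly.
3. **Sections 4.2 and 5.3:** state that daily profiles apply to inpatients and symptom-triggered profiles apply after discharge, and make the discretion sentence in 5.3 consistent with this.
4. **Analysis:** compare the collected symptoms by arm regardless of attribution. Under blinding, the randomized comparison is better evidence of a drug effect than case-by-case attribution.

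The cost is one item in a text that women already send and a study physician already reviews, plus short clarifications in 4.2 and 5.3. The downside is some nonspecific symptom reports in both arms, physician calls and occasional laboratory tests. No routine home blood draw is needed.

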3.3 Vulnerable patient populations

Pregnant women are considered a vulnerable population. As the condition of interest is a pregnancy-related and specific condition, it is unavoidable to exclude pregnant women from this research study. However, all risks to this vulnerable population will be minimized as most of the study will occur in the postpartum period. None of the study medications will be given until the patient has been postpartum for at least 6 hours.

Furthermore, neonates are considered a vulnerable population. We will be collecting data on neonatal rates on NICU admission or readmission to the hospital within 6 weeks postpartum to determine if there are any adverse effects of furosemide to the neonates. All risks to this vulnerable population will be less than minimal risk as furosemide has been used in lactating mothers previously with no neonatal adverse events noted at HUP. Also, no data currently exists in the literature to suggest that furosemide would pose any risk to breastfed infants.

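### Breastfeeding difficulty is asked at discharge only of exclusively breastfeeding women, the set of neonates followed is undefined and inconsistent, and the NICU count starts before the first dose

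*Combined protocol and SAP*

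**What the plan says.** **Breastfeeding.** Section 5.4 opens the discharge check with a condition, "If patients are breastfeeding exclusively", and then says that "research coordinators will ask the patients upon discharge if they encountered any difficulties with breastfeeding while in the hospital". At the 6-week visit, "The research coordinator will also ask questions regarding any breastfeeding issues at this time", and here no condition on feeding status is attached.

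**Neonates.** Section 5.4 says that "the charts of breastfed neonates will be followed to determine NICU admission or readmission during the first 6 weeks postpartum". Section 3.3 says "We will be collecting data on neonatal rates on NICU admission or readmission to the hospital within 6 weeks postpartum", with no restriction to breastfed infants, and gives the purpose as finding adverse effects of furosemide on neonates.

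**Timing of exposure.** Section 3.3 states that "None of the study medications will be given until the patient has been postpartum for at least 6 hours". Section 5.3 has the medication ordered by postpartum day 1, has five doses about 24 hours apart continuing after discharge, and has the coordinator record when the first pill is given. Section 3.1.3 admits deliveries from 20 weeks.

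**Analysis.** Neither outcome is named in the endpoint list (section 2.3), where the nearest item is a general one on adverse effects of furosemide. Neither has a row in the study schedule (section 5.5). Section 6.1 bases safety analyses on patients who took at least one dose and defines no breastfeeding or neonatal set.

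**The concern.** Exclusive breastfeeding at discharge is measured after randomization and after dosing has started, and it is something a diuretic could plausibly alter. A woman whose supply falls may supplement or stop. She then no longer meets the condition for being asked, so the discharge comparison is made in a group that the treatment itself may have selected, and the selection hides harm.

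The neonatal check has two separate problems. First, the set to be followed is unclear: breastfed could mean ever, currently or exclusively breastfed, no date of classification is given, and section 3.3 has no such limit at all. The denominator could therefore be settled after the data are seen. Second, the 6-week window opens at birth. Admissions in the first hours, including those of preterm infants, come before any exposure through milk and carry no information about the drug.

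At stake is how a null result would be read. Sections 3.3 and 5.3 already describe the neonatal risk as very low and the dose as safe with breastfeeding. Finding no difference on these checks could be taken as confirmation that they are too weak to give.

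**Working it through.** The plan gives no breastfeeding, difficulty or NICU rate, so there is no figure of its own to reproduce. The point rests on who is asked and which events count. The arithmetic below is illustration on assumed rates.

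**1. What each breastfeeding question can catch**

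| Contact | Who is asked | Limits |
|---|---|---|
| Discharge | Women breastfeeding exclusively | Covers time in hospital only; omits those who supplemented or stopped |
| Daily texts after discharge | All participants | Blood pressure and pill-taking only |
| 6-week visit | All who attend | Relies on recall |

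With a start by postpartum day 1 and five daily doses, the last dose falls at about day 5. The 6-week visit is at about day 42, so the gap is 42 − 5 = 37 days, or about 5 weeks.

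**2. Size of the selection at discharge**

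Take 100 women per arm who would otherwise be breastfeeding exclusively at discharge. Assume that 20 in each arm have some difficulty and continue exclusively. Let the drug cause a further s per 100 to supplement or stop before discharge. The true rate on furosemide is (20 + s)/100. The rate seen among women still exclusive is 20/(100 − s). The placebo rate is 20%.

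| s | True excess | Rate seen | Excess seen |
|---|---|---|---|
| 5 | 5 points | 20/95 = 21.1% | 1.1 points |
| 10 | 10 points | 20/90 = 22.2% | 2.2 points |
| 20 | 20 points | 20/80 = 25.0% | 5.0 points |

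If the women still exclusive instead report difficulty at exactly the placebo rate, the excess seen is 0. Both versions assume that every woman affected by the drug leaves exclusive feeding before discharge.

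**3. Which neonates are followed**

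- *Ever breastfed:* an infant exposed through milk stays in the set even if the mother later stops. Infants never breastfed have no exposure through milk.
- *Currently or exclusively breastfed:* an infant whose mother stopped because of low supply can drop out.
- *Section 3.3 as written:* all neonates are in.

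The documents do not say which applies.

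**4. Dilution by pre-dose NICU admissions**

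Arm size: 175. Section 9.1 gives 175 and a total of 385, and 2 × 175 = 350, 350 × 1.1 = 385, so 175 is per arm. The illustration assumes one followed neonate per woman. Assumed post-dose admission is 2% versus 6%.

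z = (p1 − p0) / √[p0(1 − p0)/175 + p1(1 − p1)/175]

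- Post-dose only, 2% v 6%: 0.04/√[(0.0196 + 0.0564)/175] = 0.04/0.02084 = **1.92**
- Plus 10 points, 12% v 16%: 0.04/√[(0.1056 + 0.1344)/175] = 0.04/0.03703 = **1.08**
- Plus 20 points, 22% v 26%: 0.04/√[(0.1716 + 0.1924)/175] = 0.04/0.04561 = **0.88**
- Plus 30 points, 32% v 36%: 0.04/√[(0.2176 + 0.2304)/175] = 0.04/0.05060 = **0.79**

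As a check, suppose instead that a share b of infants is admitted before the dose and only the others are at risk later, so that each arm's rate is b + (1 − b)p. For b = 0, 10%, 20% and 30% the risk ratio is 3.0, 1.31, 1.15 and 1.09, and power at two-sided 5% is 48%, 16%, 10% and 8%. The pattern is the same.

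**The case against.** A reader might infer that the safety checks as a whole exclude those harmed and that neonatal harm is looked for only in breastfed infants. The documents do not support that. The 6-week question carries no exclusivity condition, so a woman who stopped can still report it. A woman who had difficulty but is still exclusive at discharge is asked there too. The general adverse event reporting in section 7 could pick up a complaint at any time, although it does not prompt about feeding. Section 3.3 describes neonatal data without a breastfed limit, so the restriction in section 5.4 is an inconsistency rather than a settled rule. Affected infants drop out only if breastfed means currently or exclusively breastfed, or if the drug prevents breastfeeding from starting.

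A reader might also infer that early NICU admissions bias the comparison. They precede treatment and should balance by randomization, so the cost is lost sensitivity. Nor need information be lost: first-dose time is recorded, and if admission times are taken from the charts the split can be made at analysis. What is missing is the counting rule.

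Finally, every rate above is assumed, and even the clean post-dose count (z = 1.92, power 48%) would not be an adequate safety comparison. Neither outcome is a listed endpoint, and the plan announces no conclusion on lactation safety. These points lower the stakes. They leave standing the restricted discharge question, the undefined neonatal set and the missing start for the NICU count.

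**Conclusion.** The concern holds in a limited form. The discharge question is restricted by a status that treatment can change after randomization. Women who supplemented or stopped because of low supply are missed there, and the only later planned question on breastfeeding comes about 5 weeks after the last dose and only for those who attend. The set of neonates followed is undefined in section 5.4 and differs from section 3.3. The NICU count includes admissions that precede exposure.

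The size cannot be fixed from the documents. With an assumed 20% background difficulty, and with every affected woman leaving exclusive feeding before discharge, a true 10-point excess shows as about 2 points. With an assumed 2% versus 6% post-dose admission, z falls from 1.92 to between 1.08 and 0.79 for 10 to 30 points of pre-dose admissions. The first effect is selection that masks harm; the second is dilution. The primary endpoint is untouched. This is a modest weakness in secondary safety information, worth correcting because the correction is cheap.

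**What to change.** 1. At enrollment, before randomization, record whether the woman intends to breastfeed or has begun.
2. At discharge, ask every woman in that baseline group about difficulty, supplementation and stopping, and compare arms within that group.
3. Reconcile sections 3.3 and 5.4: follow the charts of all neonates, with the baseline feeding group as a prespecified subgroup, so that no later definition of breastfed decides who is counted.
4. Count only NICU admissions or readmissions that begin after the recorded first-dose time. List earlier admissions by arm as baseline.

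The cost is one baseline question, the existing discharge question put to more women at a contact already planned, chart review for more neonates, and an admission date and time from each chart. The downside is slightly more data entry. The change removes the selection and the dilution; it does not give the trial adequate power for neonatal harm, and the report should say so.
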